8.1. Descriptive Analysis

To characterize the study sample, demographic, clinical, and lab data will be described overall and by treatment arm. Categorical variables will be described using frequencies and proportions; continuous variables will be described using means and standard deviations as well

as medians and interquartile ranges (IQR) when appropriate. For the proportional odds logistic and logistic regression models, odds ratios (OR) with their 95% confidence intervals (95%CI) will be presented.

8.2. Primary outcome analysis:

Our primary analysis will be an intention-to-treat comparison of 4-month global cognition between those who receive and do not receive the cognitive training and rehabilitation intervention. The association of 4-month global cognition with the cognitive intervention vs usual care will be assessed using proportional odds logistic regression adjusting for a priori defined covariates as listed below in order of priority depending on the degrees of freedom available for each outcome:

Priority	Variable	Description
1	Pre-illness cognition	Quick Dementia Rating System is a 10-item questionnaire ranges from 0 to 30, with higher scores representing greater cognitive impairment. ^{40,41}
2	Pre-illness ADRD	Defined as a QDRS > 6, ⁴⁰⁻⁴² past history of ADRD in the electronic health record, or prescribed a home acetylcholine esterase inhibitor (i.e., donepezil) with ≥ 1 ADL impairment in the pre-illness OARS ADL. ⁴³
3	Age	Age in years at the time of enrollment
4	Pre-illness function	Older American Resources and Services Activities of Daily Living (OARS ADL) scale which assesses 7 basic and 7 instrument ADLs. ²⁹
5	Severity of illness	Acute Physiology Score of the Acute Physiology and Chronic Health Evaluation II (APACHE II) which is based on 12 laboratory, vital sign, and GCS. ⁴⁴
6	Comorbidity burden	Elixhauser comorbidity burden based on 31 comorbid conditions ⁴⁵
7	ADRD*treatment assignment interaction	To determine if cognitive intervention
8	Pre-illness Frailty	Clinical Frailty Scale (CFS) range from 0 (no frailty) to 9 (terminally ill) and is based on patient's comorbidities, and baseline cognition and function. ^{35,46}
9	Years of education	
10	Central nervous system etiology	Determined by 2 expert physician raters. Any disagreement was adjudicated by a third expert physician rater.
11	Race (Black vs non-Black)	
12	Sex	

Table 4. Covariates considered for the multivariable regression models in order of importance.

The number of covariates incorporated will depend on the number patients with completed 12-month RBANS. We will have one degree of freedom available for every 10 to 15 patients with completed outcome measurements.⁴⁷ If the number of RBANS completed (our primary outcome) is lower than expected, then we will reduce the number of covariates incorporated into the model to minimize overfitting. We will evaluate if the covariates are highly correlated with

each other; if two variables are highly correlated, the lesser priority covariate will be removed. We will not adjust for site (VUMC vs Nashville VA), because the proportion of patients enrolled in the Nashville VA is anticipated to be < 10% of those enrolled. Post-randomization covariates (e.g., interventions provided during hospitalization) will not be adjusted for because they may potentially be affected by the randomized intervention and be on the causal pathway. Unadjusted and adjusted medians with their interquartile ranges (IQR) will be reported for the intervention and usual groups. Unadjusted and adjusted odds ratio (aOR) with their 95% confidence intervals (95%CI) will also be reported.

Multiple imputation for missing covariates based on predictive mean matching will be performed. As with our previous studies, multiple imputation will also be performed for RBANS with partially missing cognitive domains.^{9,48,49} If $\leq 5\%$ of the RBANS is partially missing, then single imputation using a model-based approach will be used to calculate the RBANS global score. If $> 5\%$ of RBANS is partially missing, then multiple imputation will be performed to calculate the RBANS global score. Patients who had completely missing RBANS were removed from the statistical analysis.

8.3. Sensitivity analyses for Primary Outcome:

Several sensitivity analyses will be performed to assess the robustness of our findings:

- 1) We will perform a modified per-protocol analysis will be performed where we will determine if the total duration of cognitive training and total duration of cognitive rehabilitation is associated with our primary outcome. Participants in the usual care group will be assigned cognitive training and cognitive rehabilitation durations of 0.
- 2) We will also see if the intervention is effective in a subset of patients who are only positive for other delirium assessments (bCAM, CAM, 3D-CAM) by repeating the primary analysis on subsets of those positive for each of the listed delirium assessments.
- 3) To account for the potential differences in survival between the intervention and usual care groups, we will treat death as the worst outcome in those who died before the 4-month follow-up and assign these patients an RBANS score of 39.
- 4) To determine how multiple imputation impacted our findings, we will do a complete case analysis of patient who had missing RBANS.

We will re-run the proportional odd logistic regression models using the same covariates as our primary analysis.

8.4. Heterogeneity of treatment effect analysis for primary outcome:

Because detecting a statistical interaction may require significantly greater statistical power than detecting a main effect, a p-value for the interaction term < 0.20 will be considered as the threshold by which effect modification is potentially present. We will evaluate effect modification of the following variables:

- 1) Age
- 2) Severity of illness as defined by APS of the APACHE II
- 3) Years of education
- 4) Enrollment delirium severity (CAM-S)
- 5) Enrollment psychomotor subtype (hypoactive, hyperactive, mixed, normal)

- 6) Enrollment level of arousal (normal, decreased, increased)
- 7) Enrollment etiology (drug, infection, metabolic/endocrine, organ dysfunction, CNS)
- 8) Time from ED presentation to randomization, which is a surrogate to time to first cognitive intervention
- 9) Hopkins Rehabilitation Engagement Rating Scale (HRERS), which is a measure of patient engagement with the cognitive intervention. Patients in the usual care arm will be assigned a score of 0.

For the heterogeneity of treatment effect analysis, we will re-run the proportional odd logistic regression models using the same covariates as our primary analysis.

8.5. Analyses for Secondary Outcomes: All secondary outcomes analyses will be intention-to-treat using the same approach as our primary outcome.

- 1) Multivariable proportional odds logistic regression will be performed for executive function composite score, MoCA, OARS ADL, and EQ-5D-5L at 4-months using the same covariates.
- 2) For 4-month mortality, multivariable logistic regression will be performed. If there are less than 30 events, only a univariate analysis will be performed.
- 3) For nursing home placement, multivariable logistic regression will be performed. If there are less than 30 events, only a univariate analysis will be performed.

We will adjust for the same covariates as the primary analysis. However, the number of covariates incorporated will depend on the number patients and events for the proportional odds logistic regression and logistic regression models, respectively. For our proportional odds logistic regression model, we will have one degree of freedom available for every 10 to 15 patients with completed outcome measurements.⁴⁷ For our multivariable logistic regression models, we will have one degree of freedom available for every 10 to 15 outcomes for our multiple logistic regression models.⁴⁷ We will incorporate the covariates in order of importance. Proportions and medians with their IQR will be reported for the intervention and usual groups for categorical and continuous outcomes, respectively. Unadjusted and adjusted odds ratio (aOR) with their 95% confidence intervals (95%CI) will also be reported.

8.6. Analysis for Exploratory Outcomes (4-month and index hospitalization): All exploratory outcomes analyses will be intention-to-treat. For these outcomes, unadjusted comparisons using the Wilcoxon Rank-sum tests or chi-squared test will be performed for continuous and categorical variables, respectively. Unadjusted odds ratios will be reported. A p-value < 0.05 will be considered statistically significant.

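### The primary model can include an ADRD-by-treatment term, but the SAP does not say which treatment contrast the reported adjusted odds ratio represents

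*SAP*

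**What the plan says.** SAP 8.2 describes the primary analysis as follows: "Our primary analysis will be an intention-to-treat comparison of 4-month global cognition between those who receive and do not receive" the intervention. The association "will be assessed using proportional odds logistic regression adjusting for a priori defined covariates as listed below in order of priority". Row 7 of that list (Table 4) is "ADRD*treatment assignment interaction". It ranks ahead of frailty, education, CNS etiology, race and sex. The row's description reads "To determine if cognitive intervention" and stops there in the extracted text.

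The number of terms depends on completers: "We will have one degree of freedom available for every 10 to 15 patients with completed outcome measurements". A second rule removes the lower-priority member of any highly correlated pair of covariates. For results, "Unadjusted and adjusted medians with their interquartile ranges (IQR) will be reported for the intervention and usual groups", and "Unadjusted and adjusted odds ratio (aOR) with their 95% confidence intervals (95%CI) will also be reported".

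The covariate set is reused. SAP 8.3 states: "We will re-run the proportional odd logistic regression models using the same covariates as our primary analysis". SAP 8.4 says the same, and 8.5 adjusts for the same covariates as far as patients or events allow. ADRD is not among the effect modifiers listed in 8.4, so within the SAP its interaction appears only in the primary covariate list.

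The protocol also places the interaction in its Aim #1 formula and in Table C8.1.a without naming a contrast.

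**The concern.** Once a treatment-by-ADRD product is in the model, there is no single treatment odds ratio until someone fixes the ADRD level or the weighting at which it is read. The visible text fixes neither. With ADRD coded 0/1, the treatment coefficient that software prints is the effect in whichever stratum is coded 0.

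The SAP's objective covers patients with and without ADRD together, and 8.7 sizes the trial for one overall 6-point difference. An analyst who fits the listed model and reads off the treatment term would report a one-stratum effect as the trial's primary result, beside an unadjusted odds ratio that compares the whole arms. Another analyst, centring ADRD or omitting the product, would report the overall effect. Both would be following the visible text, and the result could differ in size, precision and significance.

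**Working it through.** **Inputs.** From SAP 8.7: SD 12.4, difference 6.0, two-sided alpha 0.05, 80% power, 51 + 102 = 153 completers, 282 enrolled, 30% death, 22% loss or withdrawal. From SAP 8.2: one df per 10 to 15 completers. Assumed, because the documents do not give them: the ADRD share p (30% to 60%, equal in both arms) and the outcome variance explained by covariates (R²).

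**Plan's own figures.** SE(overall) = 12.4 × √(1/51 + 1/102) = 2.127, and 6/2.127 = 2.82. Power is 80.6% by normal approximation and 80.05% by t-test, so 153 reproduces for one overall contrast. For enrolment, 153/(0.70 × 0.78) = 280.2, i.e. 281, or 282 when rounded to a 1:2 split.

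**Is the term admitted?** Counting one df per row, treatment plus rows 1 to 7 uses 8 df. The rule allows 153/15 = 10.2 to 153/10 = 15.3. Eight df need 80 completers (at 10 per df) to 120 (at 15 per df). The df rule therefore admits the term at the planned size. The correlation rule could still remove it or ADRD: ADRD (row 2) is partly defined by a QDRS cut-off, and QDRS is row 1.

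**What does the coefficient mean?** Proportional odds models were fitted to simulated data (n = 12,000, 10 outcome categories, half with ADRD), with true log odds ratios of 0.9 without ADRD and 0.2 with it. The treatment coefficient was 0.94 with ADRD coded 1, 0.21 with the coding reversed, 0.57 with ADRD centred and 0.57 with no interaction.

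**Cost if the coefficient is reported.** Take 6 points in both strata and no-ADRD as reference:

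SE(one stratum) = 2.127 × √(1−R²)/√(1−p); power = Φ(6/SE − 1.96).

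| ADRD share | R² = 0 | R² = 0.25 | R² = 0.50 | CI width vs overall |
|---|---|---|---|---|
| 30% | 66% | 78% | 92% | 1.20 |
| 40% | 59% | 71% | 87% | 1.29 |
| 50% | 51% | 63% | 81% | 1.41 |
| 60% | 43% | 54% | 71% | 1.58 |
| Overall contrast | about 80% | 90% | 98% | 1.00 |

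With ADRD as reference, replace 1−p by p. At R² = 0, power is then 34/43/51/59% for 30/40/50/60% ADRD. With no-ADRD as reference, the coefficient reaches 80% power only if R² is at least 0.29/0.39/0.49/0.59.

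**Check on the ordinal scale.** Proportional odds simulation, n = 153, 1,500 replicates per setting, no covariate gain, at 30/50/60% ADRD:
- model without the interaction: 78.1/77.7/77.9%
- no-ADRD coefficient: 65.3/49.4/41.1%
- contrast averaged over observed ADRD: 77.9/78.2/78.5%

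Across all settings run, including R² of 0.25 and 0.50, the averaged contrast stays within 0.6 percentage points of the model without the interaction.

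**How far it spreads.** It reaches 8.3 items 2 to 4 and the proportional odds outcomes of 8.5 when completers suffice. In 8.4 the tested modifier's own interaction term does not depend on ADRD coding, but the treatment effects read at each modifier level do. The binary outcomes need 80 to 120 events for 8 df. The SAP's figures imply 0.30 × 282 = 84.6, about 85 deaths, which allows 84.6/15 = 5.6 to 84.6/10 = 8.5 df. For mortality the term enters only at the lenient end. No event rate is given for nursing home placement.

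**The case against.** The context favours a benign reading. The primary comparison is worded by arm and by intention to treat, and adjusted medians are promised by arm. Table 4's caption says its covariates are considered, for models in the plural. Protocol Table C8.1.a sets the interaction under a separate heading that marks it as a maximum. Protocol 9.1 raises effect modification by ADRD as an additional question. The row 7 description is cut off, and text lost in extraction cannot be held against the plan.

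Much of this stands. It makes an overall effect the likely intention, and row 7 may simply be where the ADRD effect-modification question was placed. It does not settle what is reported. The sentence promising the adjusted odds ratio is intact and names no contrast, and adjusted medians by arm also need an ADRD value or distribution that is not given.

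Stronger readings are tempting but unsupported:
- That the SAP has chosen a one-stratum primary effect: it states no coding, and its objective points the other way.
- That 153 is too small: it reproduces for the overall contrast.
- That the term is certain to enter: the correlation rule and the completer count can both exclude it.
- That every secondary model is affected: the binary outcomes may not have the events.
- That the one-stratum interval is wider in every case: under severe ADRD imbalance between arms, the averaged contrast can be the wider one.

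**Conclusion.** The concern holds as an undefined contrast in the primary analysis and should be fixed before the treatment comparison is run. At the planned size the df rule admits the interaction, subject to the correlation rule, and the visible text does not say how the adjusted odds ratio is then read.

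The power loss is conditional on the raw 0/1 coefficient being reported, an equal 6-point effect in both strata, balanced ADRD and an ADRD share that the documents do not give. With covariate R² of 0.50 the coefficient still exceeds 80% power at ADRD shares up to 50% (no-ADRD as reference), so a shortfall is not inevitable. The question of which patients the estimate describes remains whatever the power. Confidence is medium, because row 7 is incomplete in the text available and the context suggests that an overall effect is meant.

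**What to change.** State in SAP 8.2 that the primary adjusted odds ratio, its confidence interval and its test come from the model without the ADRD-by-treatment term. If the term is kept, take them from a prespecified contrast averaged over the observed ADRD distribution: the treatment coefficient plus the sample ADRD proportion times the interaction coefficient.

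Test the interaction in a separate effect-modification model that keeps the ADRD main effect even if the correlation rule would remove it, and report the odds ratio and interval in each ADRD stratum. Apply the same definition wherever the primary covariate set is reused (8.3 items 2 to 4, 8.4 and 8.5), whatever the df count, so that the meaning of an odds ratio does not change with the number of completers or events.

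The cost is a few sentences and one extra model. No new data are needed. By the simulation, choosing the averaged contrast over the model without the interaction costs essentially no power.

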To assess uptake and fidelity of the cognitive training and rehabilitation, we will record the number of sessions, time taken per session, and what tasks were completed. The Cognitive Intervention Specialist will also assess patient engagement at hospital discharge and at the end of the cognitive rehabilitation intervention using the **Hopkins Rehabilitation Engagement Rating Scale (Appendix E)**.⁴² All sessions may be audiotaped (with patient consent). [name] will listen to selected cognitive training and GMT sessions within one week of their completion to (1) ensure the continued validity of the intervention of interest and (2) ensure high levels of consistency among all individuals delivering the intervention. [name] will provide feedback if the intervention administration appears suboptimal. Initially, [name] will review all recorded sessions early in the study. Once the [name] feels that the Cognitive Intervention Specialist develops mastery with cognitive training and rehabilitation protocols, spot checks will occur (~5% of recorded sessions). He will also review recorded sessions that may had issues or been problematic.

Due to COVID-19 pandemic, patients may not feel comfortable with face-to-face evaluations even after the pandemic is over. As an alternative, the cognitive training and rehabilitation intervention may be done over videoconferencing (e.g., Skype, Zoom, WebEx, FaceTime, etc.). In addition, patients or their families may not feel comfortable with research staff coming into their place of residence. Patients will have the option to come to the medical center to have their cognitive rehabilitation completed. Post-acute care facilities may also restrict visitation, even after the pandemic is over. We will attempt to do the intervention via videoconferencing in the post-acute care facility case. If not feasible, then cognitive rehabilitation will start after the patient is discharged home. These alternatives will be available to the subject for the entirety of the study. Even when the pandemic is over, some may patients or families or skilled nursing facilities may continue to have these concerns.

5.2. Prospective Data Collection – The data collected prospectively in the ED, hospital, 12-weeks post-hospital discharge, and 4-months are summarized in **Table 4**.

Prospective Data Collection	Source	Duration	ED	Hospital	12-weeks post-discharge*	4-months follow-up
Brief Confusion assessment Method (bCAM, Appendix B)	Patient	1 min	X	X		

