Confusion Assessment Method for the Intensive Care Unit (CAM-ICU, Appendix C)	Patient	1 min	X	X		
Delirium Assessment Battery (Appendix G)	Patient	5 min	X	X		
Richmond Agitation Sedation Scale (RASS, Appendix H)	Patient	Observation	X	X		
Delirium Motor Subtyping Scale-4 (DMSS-4, Appendix I)	Patient	Observation	X	X		
Confusion Assessment Method Severity (CAM-S, Appendix J)	Patient	Observation	X	X		
Blood and urine [#]	Patient	5 min	X	X		
Demographics, education, substance abuse, sensory impairment, recent hospitalization, region of residence, highest occupation, height, weight, hospitalization in past 6-months.	Patient / Informant	5 min	X			
Quick Dementia Rating Scale (QDRS, Appendix K)	Informant	3 min	X			
Everyday Cognition (eCOG, Appendix U)	Informant	5 min	X			
Montreal Cognitive Assessment (Appendix V)	Patient	5 min	X	X ^o		X
Older American Resources and Services Activities of Daily Living Scale (OARS ADL, Appendix L)	Patient / Informant	5 min	X			X
Mini-Nutritional Assessment (Appendix M)	Patient / Informant	2 min	X			
Clinical Frailty Scale (Appendix N)	Patient	Observation	X			X
Hopkins Rehabilitation Engagement Rating Scale (Appendix E)	Patient	Observation		X*	X*	
Life Space Assessment (Appendix F)	Patient/ Informant	5 min	X			X
Repeatable Battery for the Assessment of Neuropsychological Status (RBANS, Appendix O)	Patient	30 min				X

DKEFS Proverbs (Appendix P)	Patient	4 min				X
DKEFS Color-Word Interference (Appendix Q)	Patient	3 min				X
DKEFS Category Switching (Appendix R)	Patient	3 min				X
Trails A and B (Appendix W)	Patient	5 min				X
EQ-5D-5L (Appendix S)	Patient / Informant	5 min				X
Death, nursing home placement, or rehospitalization	Patient / Informant / Medical record	2 min				X
Brain MRI	Patient	45 min				X
Propositional density	Patient writing sample [^]	None	X			

Table 4. Prospective data collection schedule. ^o MOCA to be performed at 120 hours or at hospital discharge, whichever comes first. ^{\$} hospital discharge only. ^{*}To be performed at hospital discharge and after the cognitive rehabilitation sessions are completed. #, Blood and urine will be collected at enrollment and 72 hours; 120 hour blood and urine is optional. [^]Home writing samples will be used to calculate propositional density.

“Observation” in the “Duration” column indicates that these measures are obtained by observing the patient during routine research activities.

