- **Intervention:** Two daily 20-minute cognitive training sessions were administered during hospitalization with the first session occurring within 24 hours of ED presentation. The level of difficulty of the training was tailored to the patient’s current level of cognitive functioning. Cognitive rehabilitation was administered in the patient’s home within 1 week after hospital discharge. Patients received cognitive rehabilitation once a week for 12 weeks with each session lasting approximately 1 hour.
- **Usual care:** Daily delirium assessment without cognitive training occurred during hospitalization. No cognitive rehabilitation was performed in the usual care arm.

7. Outcomes

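### SAP 8.4 item 9 cannot test whether engagement (HRERS) modifies the treatment effect, because engagement is rated after randomisation and is a constant in usual care

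*SAP*

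**What the plan says.** SAP 8.4 names nine variables for the heterogeneity analysis of 4-month RBANS. The decision rule is that "a p-value for the interaction term < 0.20 will be considered as the threshold by which effect modification is potentially present". The model is fixed as well: "For the heterogeneity of treatment effect analysis, we will re-run the proportional odd logistic regression models using the same covariates as our primary analysis". That means proportional odds regression with covariates drawn from SAP Table 4.

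Item 9 is the "Hopkins Rehabilitation Engagement Rating Scale (HRERS), which is a measure of patient engagement with the cognitive intervention". For the comparator arm the SAP adds: "Patients in the usual care arm will be assigned a score of 0".

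The protocol gives the timing. In section 5.1 the person delivering the intervention will "assess patient engagement at hospital discharge and at the end of the cognitive rehabilitation intervention". The footnote to protocol Table 4 agrees: "To be performed at hospital discharge and after the cognitive rehabilitation sessions are completed". That table has no HRERS entry at enrolment. SAP section 6 confirms that usual care has delirium assessments without cognitive training, and "No cognitive rehabilitation was performed in the usual care arm".

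Item 9 does not say which of the two ratings enters the model.

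**The concern.** Effect modification asks whether the difference between arms changes across levels of a variable. The variable must therefore vary in both arms, and it should be fixed before treatment can affect it. Items 1 to 8 are baseline or enrolment variables that exist in both arms. Item 8 even substitutes time to randomisation for time to first session, which keeps the variable defined in usual care. HRERS meets neither condition. It is measured after randomisation, and in usual care it is an assigned number.

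Patients who engage well are likely to differ in prognosis from those who do not. If they score better on RBANS for reasons the covariates miss, item 9 could be reported as evidence that the intervention works in engaged patients when it works in nobody.

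**Working it through.** **1. Sample size used for the check.** SAP 8.7 gives SD 12.4, difference 6.0, two-sided alpha 0.05, 80% power and 1:2 allocation. The intervention arm needs 1.5 × (12.4 × (1.960 + 0.842) / 6)² = 50.3, so 51. Usual care needs twice the unrounded figure, 100.6, so 101, or 102 if the ratio is kept exact. This reproduces the SAP's 51 + 102 = 153. The SAP states no figure for the HRERS analysis, so 51/102 is used below.

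**2. Identification.** Let T = 1 for intervention and 0 for usual care, and let H be HRERS, with H = c for everyone in usual care. Then:

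- in the intervention arm, T×H = H;
- in usual care, T×H = 0 = H − c;
- so for every patient T×H = H − c + c×T.

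The interaction column is an exact combination of the intercept, T and H. With c = 0, as the SAP sets it, H and T×H are the same column. Numerically, the matrix [1, T, H, T×H] has rank 3 of 4 with c at 0, 10 or 25. The same matrix with a baseline modifier such as age has rank 4 of 4. The choice of 0 is therefore not the problem, since any constant fails in the same way.

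**3. What the remaining coefficient measures.** After one of the two columns is dropped, an unadjusted linear fit to simulated data gave an H coefficient of −0.22607 from all 153 patients and −0.22607 from the 51 intervention patients alone. In a proportional odds model with five outcome categories the two are close but not identical, because usual care helps to set the shared cut-points. The means were 0.330 vs 0.344, 0.542 vs 0.570 and 0.692 vs 0.742 at correlations 0.2, 0.3 and 0.4, and the two fits correlated at 0.97 to 0.99. The information on the HRERS slope comes from the intervention arm.

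**4. How often the rule would flag a null trial.** The documents give no HRERS-RBANS correlation, so r = 0.2 to 0.5 within the intervention arm is assumed. Outcomes were generated as Y = 0.6×C + 0.8×e with no treatment effect, where C is one adjusted baseline covariate with an assumed correlation of 0.6 with RBANS. HRERS was aC + be + noise in the intervention arm, with a and b set to give r and the share of r that runs through C. It was 0 in usual care. The table shows the percentage of trials with HRERS p < 0.20, where the nominal rate is 20%. The linear model used 8,000 runs per cell.

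| Model | r = 0.2 | r = 0.3 | r = 0.4 | r = 0.5 |
|---|---|---|---|---|
| Adjusted, all of r through C | about 20 | about 20 | about 20 | about 20 |
| Adjusted, three quarters through C | 24 | 30 | 36 | 47 |
| Adjusted, half through C | 37 | 51 | 69 | 85 |
| No covariates | 55 | 81 | 95 | 99 |

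The SAP's proportional odds model was checked with 15 ordered categories, a likelihood-ratio test and 600 runs per cell (Monte Carlo error about 2 points). It gave 20–22% with all of r through C, then 40, 52, 69, 84% with half, and 54, 78, 96, 99% with no covariates. The three-quarters case was not run in that model.

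**5. Hand check of one cell.** With r = 0.3 and no covariates, the pooled residual variance is (102 × 1 + 51 × 0.91) / 153 = 0.97. The expected z is 0.3 × √51 / √0.97 = 2.18. The two-sided 0.20 cut-off is 1.28, so the flag rate is about Φ(2.18 − 1.28) = Φ(0.90), or about 0.81. This agrees with the table.

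**6. Contrast with a genuine interaction test.** In a separate null simulation the engagement trait was treated as observed in both arms. The true interaction test flagged 19.6% to 21.2% of trials at the same correlations. The excess therefore comes from having engagement in one arm only.

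**The case against.** The identification point is not seriously contestable. The case on the other side concerns weight.

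- **It is exploratory.** Item 9 is one of nine modifiers, the SAP says only that modification may be present, and no decision depends on it. The screen is already loose: if nine independent null tests are run at 0.20, at least one flag appears with probability 1 − 0.8⁹ = 87%, and with eight tests 1 − 0.8⁸ = 83%. This stands, and it limits the harm. It does not make an unidentified interaction estimable.
- **The unadjusted rates are not the SAP's model.** Section 8.4 uses the primary covariates. With 153 patients and 10 to 15 patients per degree of freedom, about 10 to 15 degrees of freedom are available, so pre-illness cognition, ADRD, function and frailty could all be included. This stands. The adjusted rows are the relevant ones, and they run from no excess to 85%, depending entirely on assumptions that the documents do not inform.
- **Zero can be read as no engagement received.** SAP 8.3 item 1 likewise gives usual care zero training and rehabilitation time. There, however, zero minutes is a true value, and the analysis is presented as an association. That reading suggests item 9 was misfiled among the interactions, and it does not support keeping it there.
- **SAP 8.2 is not literally breached.** Its rule against post-randomisation variables concerns adjustment in the primary model. Item 9 conflicts with the reasoning behind that rule, not with its letter.

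**Conclusion.** The concern holds. As written, item 9 asks for an interaction that the data cannot identify, and this follows from the SAP's own coding and the protocol's schedule without any assumption. The coefficient that software would return is essentially a within-intervention-arm association between a post-randomisation rating and RBANS.

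The size of the resulting error is conditional. It rests on an assumed HRERS-RBANS correlation, a single covariate correlated 0.6 with RBANS, and an assumed share of the first correlation running through that covariate. On those assumptions the adjusted false-flag rate runs from about 20% to 85%, against a nominal 20%. Even at 20% the result would be mislabelled, because the coefficient does not measure effect modification.

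The primary comparison, the secondary outcomes and the 153-patient calculation are untouched. This is a point that should be corrected, and it does not threaten the trial's main conclusion.

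**What to change.** Remove item 9 from the SAP 8.4 list of effect modifiers and from the p < 0.20 rule. Report HRERS descriptively within the intervention arm, including its relation to RBANS if wanted. Name the rating used (hospital discharge or end of rehabilitation). State that any such relation is a non-randomised association and does not estimate effect modification.

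The cost is a change of SAP wording, with no new data and no effect on other analyses. The trial would then make no formal statement on whether engagement modifies the effect, but this design cannot support one in any case. If the question matters to the investigators, engagement predicted from baseline variables in both arms could be crossed with treatment. That would be a separate two-stage model needing its own specification, and it is not required for this correction.
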